6.5. Assessment of Tumor Response

The procedures to assess tumor response will be conducted every 8 weeks during the first 24 weeks on study and then every 12 weeks up to 72 weeks, regardless of cycle number and regardless of any dose interruptions (ie, Weeks 8, 16, 24, 36, 48, 60, 72, etc). Tumor assessments must be done any time during the specified week (+/-3 days around the week). Therefore there is a 13-day window to conduct tumor assessments that begins 3 days prior to the start of the last week of the corresponding 28-day cycle and ends 3 days after the last day of that same corresponding cycle. The description of the assessments to be conducted are detailed in Section [6.12](#) and outlined in the Study Procedures Table in [Appendix 2](#).

A bone marrow biopsy and aspirate will be collected for all subjects who achieve a CR for confirmatory purpose. For LPL/WM without adenopathy and CLL subjects a bone marrow biopsy/aspirate will be collected to confirm a PD if based only upon declines in the platelet count and/or hemoglobin for CLL subjects or rise in Serum monoclonal IgM in LPL/WM. For all LPL/WM patients who achieve CR or PD and are not evaluable by radiological criteria require confirmation by bone marrow evaluation. If the subject does not otherwise meet criteria for CR or if the nature of PD does not require bone marrow confirmations, it is not necessary to obtain a bone marrow biopsy/aspirate (See Sections [6.20](#) and [6.21](#)).

ONLY for subjects with LPL/WM, an evaluation of serum monoclonal IgM by both SPEP and IFE will be conducted including cryoglobulin testing (LPL/WM enrollment limited to those sites which have cryoglobulin analysis capabilities). Serum monoclonal IgM as assessed by SPEP will only be considered if baseline total serum IgM quantitation by nephelometry is not available.

This procedure should be conducted on the Day 1 visit occurring during the week window allotted for tumor response assessments. LPL/WM subjects who do not have lymphadenopathy on their screening CT/MRI evaluations are not required to have repeated scans for tumor assessment unless clinically indicated, but all subjects in this subset will require BM evaluations for suspected PD or CR assessments.

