8.4.2. Calculation of Tumor Control Variables

Tumor control assessments will be based on standardized response and progression criteria for NHL {Cheson 2007} and CLL {Hallek 2008}, as specifically modified for this study considering the pharmacology of GS-9973 {Cheson 2012}. The individual and composite endpoints of response and progression (considering changes in lymph node area, liver and spleen size, bone marrow, platelet counts, hemoglobin, neutrophil counts, and peripheral blood lymphocyte counts) will be determined. Tumor control will be documented at each assessment by response category (eg, CR, PR, SD, definitive PD) as defined for each response parameter, SPD value, percentage change in SPD values from baseline or nadir, date that response is first documented, date that response is confirmed, and date of disease progression.

Changes in tumor status as provided by the investigator and changes in tumor status as adjudicated by the IRC (see Section 9.4) will be described and compared. The findings of the IRC will be considered primary for analyses of all tumor control endpoints.

For time-to-event endpoints of PFS and DOR, the following censoring conventions will be applied:

- Data from surviving, non-progressing subjects will be censored at the earliest of the time of initiation of antitumor treatment other than the study treatment or the last time that lack of definitive progression was objectively documented.
- Data from subjects who have disease progression or die after ≥ 2 consecutive missing tumor assessments will be censored at the last time prior to the missing assessments that lack of definitive disease progression is objectively documented.

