8.5.4. Exploratory Analyses

CCI

CCI

8.6. Continuous Data Review of PFS Endpoint Rate at 16 weeks (CLL after BCR Targeted Therapy, MCL and DLBCL) or 24 weeks (CLL and FL)

For subjects with MCL, DLBCL, CLL (except for the CLL dose ranging cohort), and FL, a Bayesian, continuous data review approach using a Beta-Binomial model ([\(Thall 1994\)](#)) will be used to update the estimates of the PFS rates at 16 weeks (CLL after BCR targeted therapy, MCL and DLBCL) or 24 weeks (CLL and FL) and, therefore, assess efficacy once each subject's primary endpoint becomes available for a malignancy. The Bayesian analysis method will be applied separately to each of the MCL, DLBCL, FL cohorts and the CLL cohorts (except for the CLL dose ranging cohort).

In this model, response is defined as a subject not experiencing progression or death by Week 16 (CLL after BCR targeted therapy, MCL and DLBCL) or week 24 (CLL and FL). Only subjects with known progression/death status at Week 16 (CLL after BCR targeted therapy, MCL and DLBCL) or week 24 (CLL and FL) are included in the analysis. Subjects who withdraw or are lost to follow-up before Week 16 (CLL after BCR targeted therapy, MCL and DLBCL) or week 24 (CLL and FL) will be considered as a non-responder for the analysis. In this Beta-Binomial model, a binomial likelihood for the data and a conjugate Beta (0.5, 1.5) prior distribution for response rate θ are assumed. Statistical inference and decision-making will be based on the posterior distribution of response rate θ , which is a Beta distribution with parameters $x+0.5$ and $n-x+1.5$, where x is the observed number of subjects who achieve the response and n is the total number of subjects who have a response result for a given malignancy. More details about the Bayesian design and analysis model will be provided in the statistical analysis plan (SAP).

The Bayesian model will be fit to the data sequentially as subjects' response status becomes available; decisions based on the estimate of response rate will be made accordingly. The posterior distribution of the response rate θ in each malignancy will be provided on an ongoing basis and at the end of the trial. Let $\text{Pr}(\theta < 0.2 | \text{data})$ denote the probability that the response rate θ is less than 0.2 given the current data. The decision rules and actions to be taken based on the updated posterior distribution of response rate θ given the current data are as follows:

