## **6. EFFICACY ANALYSES**

### **6.1. Primary Efficacy Endpoint**

#### **6.1.1. Definition of the Primary Efficacy Endpoint**

The primary efficacy endpoint of this study is PFS rate at 16 weeks (CLL after BCR targeted therapy, MCL, and DLBCL) or 24 weeks (CLL and iNHL). PFS is defined as the interval from the first dose of ENTO to the earlier of the first documentation of definitive disease progression or death from any cause.

The determination of NHL response and progression (defined in the Protocol Section 6.20) is based on standardized criteria {Cheson 2007, Rourke 2010} as specifically modified for this study to reflect the biology of the diseases under study and the pharmacology of ENTO and the methods to be used in evaluation. The determination of CLL response and progression (defined in the Protocol Section 6.21) is based on standardized IWCLL criteria {Hallek 2008} as specifically modified for this study considering the pharmacology of ENTO and the methods to be used in evaluation.

In accordance with the Gilead Protocol 339-0102 Imaging Charter, if there is uncertainty regarding whether there is true progression, the subject may continue study treatment and remain under close observation (eg, evaluated at 4-week intervals). If subsequent evaluations suggest that the subject is experiencing progression, then the date of progression should be the time point at which progression was first identified. A single PD determination followed by a determination that indicated either no change or improvement in disease prior to the single PD observation will not be considered as PD.

Subjects without progression or death will be censored at the last adequate post-baseline tumor assessment time. If subjects receive other anti-cancer therapy or have  $\geq 2$  consecutive missing post-baseline tumor assessments immediately before documented progression or death, they will be censored at the last adequate post-baseline tumor assessment time before starting anti-cancer therapy or before  $\geq 2$  consecutive missing tumor assessments whichever is earlier. If subjects don't have adequate baseline tumor assessment or adequate post-baseline tumor assessment, they will be censored on the date of Study Day 1 unless subjects die before or on the 2nd scheduled post-baseline tumor assessment without receiving other anti-cancer therapy. Please see [Appendix 2](#) for details on PFS event and censoring time derivation.

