#### **6.1.2. Analysis of the Primary Efficacy Endpoint**

The primary analysis of PFS will be performed using the Kaplan-Meier (KM) method based on IRC response assessments for the FAS. Medians, Q1, Q3 of the PFS distributions, and the proportion of subjects who are progression-free at Week 16 (for CLL after BCR targeted therapy, MCL, and DLBCL) and Week 24 (for CLL and iNHL) from the first dosing date will be

provided along with corresponding 95% confidence intervals (CIs). The loglog transformation will be used to compute the CIs.

PFS rate of the CLL prior BTK inhibitor exposure and CLL prior PI3K inhibitor exposure cohorts will be estimated separately. PFS rate of the CLL dose ranging cohort will be estimated by dose levels.

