## Appendix 2. PFS Definition and Derivation Diagram

Progression-free survival (PFS) is defined as the interval from the first dosing date of study drug to the earlier of the first documentation of definitive disease progression or death from any cause.

Definitive disease progression for NHL is defined in the Protocol Section 6.20 based on standardized criteria {Cheson 2007, Rourke 2010} as specifically modified for this study to reflect the biology of the diseases under study and the pharmacology of study drug and the methods to be used in evaluation. The determination of CLL response and progression is defined in the Protocol Section 6.21 based on standardized IWCLL criteria {Hallek 2008} as specifically modified for this study considering the pharmacology of ENTO and the methods to be used in evaluation. The progression should be identified by relevant radiographic imaging assessments and pertinent clinical data by IRC and investigators. For this study, the IRC assessments will be used as primary PFS analyses. The date of definitive progression will be the time point at which progression is first identified. The death from any cause to be considered as PFS event should occur within the time window of 2 consecutive scheduled post-baseline tumor assessments after the last tumor assessment.

Subjects without progression or death will be censored at the last adequate post-baseline tumor assessment time. The adequate tumor assessments for determining censoring dates include complete response (CR), partial response (PR), minor response (MR), stable disease (SD), progressive disease (PD), and very good partial response (VGPR) or minor response (MR) for subjects with LPL/WM. Non-evaluable (NE), not assessed, and not applicable are considered as not adequate.

Subjects will be censored on the date of Study Day 1 if

- no adequate baseline tumor assessment is available and subject didn't die before or on the 2nd scheduled post-baseline tumor assessment without receiving anti-cancer therapy;
- or if no adequate post-baseline tumor assessment is available and subjects didn't die
- or if no adequate post-baseline tumor assessment is available and subjects died after the 2nd scheduled tumor assessment.

Subjects will be censored on the date of last adequate post-baseline tumor assessment, or Study Day 1 if the last adequate post-baseline tumor assessment doesn't exist, for the following situations:

- who do not have documented progression or die, or

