- who start new anti-cancer therapy before documented progression, or
- who start new anti-cancer therapy before death without documented progression, or
- who have  $\geq 2$  consecutive missing post-baseline tumor assessments immediately before documented progression, or

- who have  $\geq 2$  consecutive missing post-baseline tumor assessments immediately before death without documented progression

Table 13-1 below lists detailed event/censoring scheme for PFS derivation and the derivation diagram lists all decisions on event/censoring indicators and time.

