**Table 13-1. Event/Censoring Scheme of Analysis for PFS**

PFS Derivation Step	Situation	Date of Progression or Censoring	Outcome
1	No adequate baseline tumor assessments and subjects didn't die before or on the 2nd scheduled post-baseline tumor assessment	Study Day 1*	Censored
1	No adequate baseline tumor assessments and subjects died before or on the 2nd scheduled post-baseline tumor assessment without receiving anti-cancer therapy	Date of death	Event
1	No adequate baseline tumor assessments, subjects died before or on the 2nd scheduled post-baseline tumor assessment and received anti-cancer therapy	Study Day 1*	Censored
2	No adequate post-baseline tumor assessments and subjects did not die	Study Day 1	Censored
2	No adequate post-baseline tumor assessments and subjects died after the 2nd scheduled post-baseline tumor assessment	Study Day 1	Censored
2	No adequate post-baseline tumor assessments and subjects died before or on the 2nd scheduled post-baseline tumor assessment without receiving anti-cancer therapy	Date of death	Event
2	No adequate post-baseline tumor assessments, subjects died before the 2nd scheduled post-baseline tumor assessment and received anti-cancer therapy	Study Day 1	Censored
3	Documented progression and didn't receive anti-cancer therapy or have $\geq 2$ consecutive missing post-baseline tumor assessments immediately before documented progression	Date of the first documented progression	Event
3	Death without progression and within the time window of 2 consecutive scheduled post-baseline tumor assessments after the last tumor assessment and didn't receive anti-cancer therapy or have $\geq 2$ consecutive missing post-baseline tumor assessments immediately before death	Date of death	Event
3	No documented progression or death and didn't receive anti-cancer therapy or have $\geq 2$ consecutive missing post-baseline tumor assessments	Date of the last adequate post-baseline tumor assessment	Censored

[figure not shown]
PFS Derivation Step	Situation	Date of Progression or Censoring	Outcome
4	Start new anti-cancer therapy without or before documented progression or death or have $\geq 2$ consecutive missing post-baseline tumor assessments immediately before documented progression or death	The later one of 1) Date of the last adequate post-baseline tumor assessment on/prior to the new anti-cancer therapy start date and/or the consecutive missing 2) Study Day 1	Censored

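### In the Week 24 cohorts, the two-missed-scans rule censors at Study Day 1 a subject whose progression by Week 24 is documented after missed Week 8 and 16 scans, so a known failure drops out of the primary rate

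*SAP*

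**What the plan says.** SAP 6.1.1 sets the primary endpoint as the PFS rate at 16 weeks for CLL after BCR-targeted therapy, MCL and DLBCL, "or 24 weeks (CLL and iNHL"). SAP 6.1.2 gives the estimator: "The primary analysis of PFS will be performed using the Kaplan-Meier (KM) method based on IRC response assessments for the FAS". Protocol 6.5 schedules scans "every 8 weeks during the first 24 weeks on study and then every 12 weeks up to 72 weeks", that is, at Weeks 8, 16 and 24 and then at longer intervals.

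SAP Appendix 2 censors subjects who have two or more "consecutive missing post-baseline tumor assessments immediately before documented progression". The date is the last adequate post-baseline assessment, "or Study Day 1 if the last adequate post-baseline tumor assessment doesn't exist". Table 13-1 step 4 gives the date as "The later one of 1) Date of the last adequate post-baseline tumor assessment on/prior to the new anti-cancer therapy start date" and/or the run of missed scans, or Study Day 1 if that is later. SAP 6.1.1 also places the date before the missed run. Protocol 8.4.2 has the same rule: such data "will be censored at the last time prior to the missing assessments that lack of definitive disease progression is objectively documented".

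SAP 6.3 drops all sensitivity analyses. SAP 6.1.1 puts investigator assessments in listings only.

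**The concern.** Two missed scans blur when progression happened. They do not blur whether it had happened by a landmark at or after the scan that shows it. Censoring after a gap protects a PFS curve against late-dated events. Applied to a landmark that the subject is already known to have failed, it removes a failure from the estimate.

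The censoring also depends on the outcome. Take two subjects who both miss Weeks 8 and 16 and start no other therapy. If the Week 24 scan shows stable disease, step 4 is not triggered, because it needs progression or death directly after the gap. The Appendix 2 text then follows that subject to the last adequate scan, and the subject supports the Week 24 rate. If the Week 24 scan shows progression, the subject leaves on Day 1. Kaplan-Meier assumes that censoring carries no information about outcome; here it does, and it favours the drug. No planned analysis puts the failure back.

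**Working it through.** **Inputs.** Landmark: Week 24 (SAP 6.1.1), which is Day 6 x 28 = 168. Scans before it: Weeks 8 and 16 (Protocol 6.5). Cohort sizes: up to 40 for CLL and FL, and 20 per dose level in the dose-ranging cohort (Protocol 8.7). The number m of subjects who miss Weeks 8 and 16 and have IRC progression by Week 24 is not in the documents; I vary it.

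**The plan's own figures.** No stated figure tests this rule. As a check on reading the futility model, an exact calculation (Beta(0.5, 1.5) prior, a look after each subject from 10 to 40, stop if the posterior probability that the rate is below 0.2 exceeds 0.9) gives a futility probability of 0.8371 at a true rate of 0.10, against 0.8408 from simulation in Protocol Table 8-3. At 0.20 it gives 0.3189 against 0.3162. The point below does not depend on these.

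**Path through Table 13-1** for a subject who misses Weeks 8 and 16 and has IRC progression by Day 168:
- Step 2 (no adequate post-baseline scan) does not apply, because Appendix 2 counts a progression assessment as adequate.
- Step 3 does not give an event, because it excludes progression directly after two or more missed scans.
- Step 4 applies. No adequate scan precedes the gap, so the date is Study Day 1 and the outcome is censored.

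**Effect on the estimate.** A subject censored on Day 1 leaves the risk set before the first scan-time event. With x of n truly progression-free and no other censoring before Week 24:

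- counted as events: rate = x/n
- SAP rule: rate = x/(n - m)

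| x/n | As events | m = 1 | m = 2 |
|---|---|---|---|
| 8/40 | 20.0% | 8/39 = 20.5% | 8/38 = 21.1% |
| 16/40 | 40.0% | 16/39 = 41.0% | 16/38 = 42.1% |
| 6/20 | 30.0% | 6/19 = 31.6% | 6/18 = 33.3% |
| 8/20 | 40.0% | 8/19 = 42.1% | 8/18 = 44.4% |

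A direct Kaplan-Meier calculation at Day 168 with log-log limits confirms the formula. For 8/40, 20.0% (95% CI 9.4-33.5) becomes 21.1% (9.9-35.0) with m = 2. For 6/20, 30.0% (12.3-50.1) becomes 33.3% (13.7-54.5).

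**Alternative reading of the date.** Because Appendix 2 lists progression as an adequate assessment, its text alone could put the censoring date at the progression scan. SAP 6.1.1 and step 4 place it before the gap. On either reading the subject is not an event.

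**Futility model.** Protocol 8.6 defines a response as no progression or death by the landmark and restricts the review to "Only subjects with known progression/death status at Week 16" or Week 24, with withdrawals and losses counted as non-responders. This subject's status is known, so the review would count a non-responder.

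**The case against.** The strongest reply is that the rule is prespecified in Protocol 8.4.2, is conventional, and belongs to a Kaplan-Meier analysis rather than a binary proportion. That is true, but it does not answer censoring that depends on the outcome and can move the primary rate in one direction only.

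The reply on size largely stands. Subjects attend every 28 days, tumour status is assessed clinically at each visit, and symptoms prompt imaging, so few will miss both scans and still be imaged by Week 24. At an observed 40%, Protocol Tables 8-1 and 8-2 give credible intervals of 25.3-54.3% (n = 40) and 19.9-59.3% (n = 20), far wider than a shift of 1.0 or 2.1 points. The study is exploratory, the report is synoptic, and by-subject listings would show any such case.

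Three stronger readings are tempting, and the documents do not support them.
- A reader might infer that the reported rate conflicts with the futility rule in every affected cohort. The dose-ranging and Other iNHL cohorts have no futility review (Protocol 3.1.2 and 3.1.3). For original CLL and FL the two methods already differ by design, because the review counts withdrawals as non-responders while the final analysis censors. The note to Protocol Table 5-1 closes those cohorts to enrolment, so no continuation decision is now affected.
- A reader might extend the point to the Week 16 cohorts. Weeks 8 and 16 cannot both be missed before progression documented by the Week 16 scan, and progression first seen at Week 24 is not a certain Week 16 failure.
- A reader might treat every progression at the Week 24 scan as a failure at Day 168. The scan window in Protocol 6.5 runs to 3 days after the cycle ends, Day 171. Progression on Days 169-171 is in window but after Day 168.

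**Conclusion.** The point holds for the Week 24 cohorts only: original CLL, the CLL dose-ranging arms, FL and Other iNHL. There the censoring rule takes a known failure out of the primary estimate, and the error can only raise the rate. Per affected subject at 40%, the shift is 1.0 point with n = 40 and 2.1 points with n = 20. These figures assume no other censoring before Week 24. They also rest on m, which is a judgement (probably 0 to 2); if m is zero, nothing changes. For original CLL and FL only, the futility model would count the same subject as a non-responder. The expected effect is small, but it sits on the primary endpoint with no backup analysis, so it should be corrected.

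**What to change.** In SAP 6.1.1 and Table 13-1 step 4, state that for the Week 24 PFS rate only, IRC progression documented on or before Day 168 is an event whatever the number of missed scans before it. State also how progression at an in-window Week 24 scan on Days 169-171 is assigned. Keep the two-missed-scans censoring for progression documented after the landmark, and for the median and quartiles. No Week 16 wording is needed. List the change in SAP 6.3, because it departs from Protocol 8.4.2.

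The cost is a separate event flag for the rate, so that the rate and the quartiles come from slightly different derivations, and a reported rate that stays the same or falls slightly.

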**Table 13-1. Event/Censoring Scheme of Analysis for PFS**

PFS Derivation Step	Situation	Date of Progression or Censoring	Outcome
1	No adequate baseline tumor assessments and subjects didn't die before or on the 2nd scheduled post-baseline tumor assessment	Study Day 1*	Censored
1	No adequate baseline tumor assessments and subjects died before or on the 2nd scheduled post-baseline tumor assessment without receiving anti-cancer therapy	Date of death	Event
1	No adequate baseline tumor assessments, subjects died before or on the 2nd scheduled post-baseline tumor assessment and received anti-cancer therapy	Study Day 1*	Censored
2	No adequate post-baseline tumor assessments and subjects did not die	Study Day 1	Censored
2	No adequate post-baseline tumor assessments and subjects died after the 2nd scheduled post-baseline tumor assessment	Study Day 1	Censored
2	No adequate post-baseline tumor assessments and subjects died before or on the 2nd scheduled post-baseline tumor assessment without receiving anti-cancer therapy	Date of death	Event
2	No adequate post-baseline tumor assessments, subjects died before the 2nd scheduled post-baseline tumor assessment and received anti-cancer therapy	Study Day 1	Censored
3	Documented progression and didn't receive anti-cancer therapy or have $\geq 2$ consecutive missing post-baseline tumor assessments immediately before documented progression	Date of the first documented progression	Event
3	Death without progression and within the time window of 2 consecutive scheduled post-baseline tumor assessments after the last tumor assessment and didn't receive anti-cancer therapy or have $\geq 2$ consecutive missing post-baseline tumor assessments immediately before death	Date of death	Event
3	No documented progression or death and didn't receive anti-cancer therapy or have $\geq 2$ consecutive missing post-baseline tumor assessments	Date of the last adequate post-baseline tumor assessment	Censored

[figure not shown]
PFS Derivation Step	Situation	Date of Progression or Censoring	Outcome
4	Start new anti-cancer therapy without or before documented progression or death or have $\geq 2$ consecutive missing post-baseline tumor assessments immediately before documented progression or death	The later one of 1) Date of the last adequate post-baseline tumor assessment on/prior to the new anti-cancer therapy start date and/or the consecutive missing 2) Study Day 1	Censored

\* Study Day 1 is the day of first dose of study drug administration.

When the date of initiation of anti-cancer therapy other than the study treatment is incomplete or missing, the following algorithm will be followed:

- If the day is missing but the month and year are available, then the imputed day will be the first day of the month.
- If day and month are missing but year is available, then the imputed day and month will be 01Jan or the last day of the month for the last adequate disease assessment if they have the same year, whichever is later.

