### **6.2.2.2. Duration of Response**

DOR analysis will be conducted in the responding subjects of FAS set. Responding subjects are those who achieve a CR or PR (or VGPR/MR for LPL/WM subjects). The censoring rule is same as PFS analyses (see [Appendix 2](#)).

DOR will be summarized using the KM method. The KM estimates of the DOR survival function will be presented. The median of DOR will be provided along with the corresponding 95% CIs. Additionally, the Q1 and Q3 will also be provided. The log-log transformation will be used to compute the CIs.

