#### 7.1.5.2. Incomplete Dates

If the onset date of the AE is incomplete and the AE stop date is not prior to the first dosing date of study drug, then the month and year (or year alone if month is not recorded) of onset determine whether an AE is treatment emergent. The event is considered treatment emergent if both of the following 2 criteria are met:

- The AE onset is the same as or after the month and year (or year) of the first dosing date of study drug, and
- The AE onset date is the same as or before the month and year (or year) of the date corresponding to 30 days after the date of the last dose of study drug

An AE with completely missing onset and stop dates, or with the onset date missing and a stop date later than the first dosing date of study drug, will be considered to be treatment emergent. In addition, an AE with the onset date missing and incomplete stop date with the same or later month and year (or year alone if month is not recorded) as the first dosing date of study drug will be considered treatment emergent.

In case when the AE onset date is incomplete and needs to be imputed, the following algorithm will be followed:

- If the day is missing but the month and year are available, then the imputed day will be the first day of the month or the first dosing date if they have the same month and year, whichever is later.
- If the day and month are missing but year is available, then the imputed day and month will be 01Jan or the first dosing date if they have the same year, whichever is later.

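### A new-therapy start with a missing day is set to the 1st of the month without a check against progression, so a true progression in that month can be censored in PFS and DOR

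*SAP*

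**What the plan says.** Below Table 13-1, SAP Appendix 2 gives two rules for an incomplete start date of non-study anti-cancer therapy.

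- Month and year known: "If the day is missing but the month and year are available, then the imputed day will be the first day of the month".
- Only the year known: the imputed day and month are "01Jan or the last day of the month for the last adequate disease assessment if they have the same year, whichever is later".

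The second rule has a guard, because the date cannot fall before the month of the last adequate assessment in that year. Progression counts as such an assessment: "The adequate tumor assessments for determining censoring dates include complete response (CR), partial response (PR), minor response (MR), stable disease (SD), progressive disease (PD" and the list continues.

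In Table 13-1, step 3 makes a documented progression an event if no new therapy came first. Step 4 covers the situation "Start new anti-cancer therapy without or before documented progression or death". It censors at the later of Study Day 1 and the "Date of the last adequate post-baseline tumor assessment on/prior to the new anti-cancer therapy start date". SAP 6.2.2.2 carries this over to duration of response: "The censoring rule is same as PFS analyses".

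On the secondary matter, Protocol 8.6 says that the posterior distribution of the Week 16 or Week 24 rate will be given during the trial and at its end, and leaves further Bayesian detail to the SAP. SAP 6.1.2 plans Kaplan-Meier estimates only. SAP 6.3 lists only the sensitivity analyses as dropped. SAP 1.2.2 refers to Section 2.1 for details of the futility boundary, and Section 2.1 contains none.

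**The concern.** The usual sequence is progression first and new therapy afterwards. When both fall in one calendar month and the therapy day is not recorded, the day-missing rule can reverse that order. The subject then moves from step 3 (event) to step 4 (censored), and the censoring date goes back to an earlier scan. The less complete record, with only the year, would keep the event when progression is the last adequate assessment.

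The primary endpoint and duration of response are affected, in cohorts of at most 40 subjects, or 20 for Richter's. No planned table would show it: SAP 7.6 lists post-treatment therapies without summarizing them, and SAP 6.3 drops the sensitivity analyses.

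The secondary matter is one of reporting. Protocol Tables 8-1 to 8-3 justify the cohort sizes on a binary rate in which withdrawals count as non-response. No planned output reports that rate.

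**Working it through.** **1. The plan's own figures.** Protocol 8.6 gives the posterior as Beta(x+0.5, n−x+1.5). For 8 of 40 this is Beta(8.5, 33.5), with mean 8.5/42 = 0.202 and 95% credible interval 0.097 to 0.335, as in Table 8-1. All rows of Tables 8-1 and 8-2 reproduce to within 0.001. Table 8-3 at a true rate of 0.10 gives 0.837 by exact calculation against 0.8408 by simulation. No sample-size figure is in question. The plan states no figure for the date rule.

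**2. The rules applied to one case.** Progression on 15 March, therapy truly started on 25 March, progression the last adequate assessment.

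| Therapy start recorded as | Date used | Status |
|---|---|---|
| 25 March | 25 March | Event on 15 March |
| March and year | 1 March | Censored at the last adequate scan on or before 1 March, or Study Day 1 |
| Year only | 31 March | Event on 15 March |

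The fault is confined to progression. For a subject "who start new anti-cancer therapy before death without documented progression", therapy did come before death, so the imputed day can move the censoring date but not the status.

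**3. How often, given a missing day.** Assume progression dates spread evenly over 2013 to 2016 (48 months, 1,461 days) and a fixed gap of g days to therapy. In a month of L days, progressions on days 2 to L−g are misordered, which is L−g−1 days (not below zero).

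- g = 7: (1,461 − 48×8)/1,461 = 74%
- g = 14: (1,461 − 48×15)/1,461 = 51%
- g = 21: (1,461 − 48×22)/1,461 = 28%
- g = 28: 28 months of 31 days give 2 days each and 16 months of 30 days give 1 each, so 72/1,461 = 5%
- g = 30 or more: none

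**4. Size in the Kaplan-Meier rate.** Assumed cohort of 40: 12 progressions at Week 8, 12 at Week 16, 16 subjects progression-free. The Week 16 rate is (28/40)×(16/28) = 40.0%.

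- One Week 16 progression censored at Week 8: 0.700×16/27 = 41.5%.
- One Week 8 progression censored at Study Day 1: 16/39 = 41.0%.
- Cohort of 20 (6 and 6 progressions), one Week 16 progression lost: 0.700×8/13 = 43.1%.
- Week 24 cohort of 40 (8 progressions at each of Weeks 8, 16 and 24), one Week 24 progression lost: 0.600×16/23 = 41.7%.
- One progression dated just after the Week 16 landmark, censored at Week 8: 0.700×(1 − 12/27) = 38.9%. Such dates can occur: cycle 4 ends on Day 112 and the scan window in Protocol 6.5 runs 3 days longer, to Day 115.

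**5. Kaplan-Meier against the binary rate.** Assume 8 of 40 progression-free, L early leavers, and the remaining progressions split equally between Weeks 8 and 16. The binary rate is 20.0% whatever L is.

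- L = 4: Kaplan-Meier is 8/36 = 22.2% if they leave before the first scan, or 0.650×8/22 = 23.6% if they leave after Week 8.
- L = 8: 8/32 = 25.0%, or 0.700×8/20 = 28.0%.

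The posterior is therefore not a restatement of the Kaplan-Meier result.

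**The case against.** The strongest reply is that this will seldom happen. It needs a missing day and therapy in the same calendar month as progression. Protocol 6.6 keeps subjects on study drug until the independent review confirms progression. Where progression is uncertain, Protocol 6.20.7.7 and 6.21.5.4 allow re-evaluation, for example at 4-week intervals, and date progression back to the assessment at which it initially appeared. IgM-based progression needs confirmation at least 6 weeks apart. All of this lengthens the gap. SAP 2.1 has queries resolved before the final analysis, which should reduce missing days. One lost event is also small beside the interval of 0.253 to 0.543 that Table 8-1 gives at 40%, in a study that Protocol 8.8 calls exploratory.

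The argument on frequency stands. At a 28-day gap, one expected loss needs about 1/0.049 = 20 progressions with a missing therapy day. Even at 14 days, three losses need about 3/0.507 = 6. It does not make the rule right: Protocol 6.6 lets a subject move to other treatment at once when the medical condition requires it, so short gaps are foreseeable.

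A reader might cite the adverse-event rule in SAP 7.1.5.2 as the same guard applied elsewhere. It is not a parallel. That rule takes the "first day of the month or the first dosing date if they have the same month and year, whichever is later", so it floors at first dosing and not at an outcome assessment. Unless first dosing fell in March, it would still give 1 March in the example. The relevant inconsistency is with the year-only bullet.

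On the posterior, the promise sits in the section on continuous review and not in the efficacy plan, the SAP serves a synoptic report, and the posterior is closed-form once x and n are known. That makes it secondary, but does not explain why SAP 6.3 is silent.

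**Conclusion.** The point holds and is worth correcting before the database is finalized. Followed exactly, the day-missing rule gives the wrong event status for a progression after the 1st of a month in which new therapy later began. The text alone establishes this. The size rests on assumptions, because the documents give neither the number of missing days nor the gap to therapy. Under the illustrative cohorts, one lost event moves 40.0% by about 1 to 3 percentage points upward, or about 1 point downward if it falls just after the landmark.

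Three stronger readings are tempting and not supported.

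- That the primary result is materially inflated. The frequency is unknown and probably low, and the direction is not always upward.
- That the SAP replaced the protocol's primary analysis. Protocol 8.5.2.1 already makes Kaplan-Meier primary. What is missing is the promised end-of-trial posterior, a declaration of its removal, and a working pointer from SAP 1.2.2.
- That the SAP's wider wording of censoring at new therapy, compared with Protocol 8.4.2, alters the result. Protocol 6.5 and 6.6 end follow-up around the start of the next treatment, so this is a documentation matter only.

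**What to change.** In SAP Appendix 2, for a therapy start with a missing day:

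- if the first documented progression falls in the recorded month, impute the last day of that month, or the day after progression, whatever later scans exist;
- if there is no progression in that month but an adequate assessment falls in it, impute the last day of the month;
- otherwise keep the 1st.

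Tie the year-only rule to the first documented progression in the same way. A guard tied to the last adequate assessment is not enough. SAP 6.2.1 foresees assessments after other therapy; with a further scan in April, the last adequate assessment would no longer be in March and 1 March would be imputed again. The year-only rule has the same weakness when a later scan falls in the next calendar year.

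For each cohort under Bayesian review, add to SAP 6.1.2 the binary Week 16 or Week 24 rate with withdrawals as non-responders, and the Beta(0.5, 1.5) posterior mean and 95% credible interval, beside Kaplan-Meier. Alternatively, declare the omission in SAP 6.3. Put the boundary details in Section 2.1 or correct the pointer in SAP 1.2.2. A line in SAP 6.3 can note the wider wording of censoring at new therapy.

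The cost is a few lines of text and, if chosen, one small table. The revised rule may occasionally keep an event where therapy truly came first. The binary rate will be equal to or below the Kaplan-Meier rate when subjects leave early, so the table needs a note saying why.
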